STUDY PROTOCOL & STATISTICAL ANALYSIS PLAN

Official title: MOTIVATE: Moving to Improve Chronic Back Pain and Depression in Older Adults

NCT number: NCT03914469

IRB Approved date: 06-10-21

The University of Texas Southwestern Medical Center at Dallas Institutional Review Board

Title: MOTIVATE: Moving to Improve Chronic Back Pain and Depression in

Older Adults

Principal Investigator: [name]- Principal Investigator

Funding Source: Institutional funds

Purpose and Objectives

The overarching goal of this study is to evaluate a tele-based behavioral change intervention for older adults (aged 50 years and older) with chronic low back pain (cLBP) and comorbid depression, and to ultimately assess its effect on cLBP-related disability and depressive symptoms.

Specific Aims: Behavioral interventions for older adults with comorbid chronic low back pain (cLBP) and depression are urgently needed. Our group developed a telephone delivered intervention targeting behavioral constructs common to both cLBP and depression in older adults: MOTIVATE (Moving to Improve Back Pain and Depression in Older Adults). Further, we emphasize individualized values, goals and motivations to change behavior- all relevant for sustaining behavior change. We now seek to 1) evaluate the feasibility of MOTIVATE in a diverse older adult population, and 2) inform future research and trial design choices by eliciting feedback from key stakeholder groups. These results will inform methods and procedures for use in a large-scale, R01 level hybrid (Type 1) effectiveness-implementation randomized controlled trial (RCT).

Aim 1: Evaluate the feasibility of implementing MOTIVATE (n=25) vs. waitlist control (n=25) among older adults with comorbid cLBP and depression.

Aim 2: Ascertain key barriers and facilitators to implementing MOTIVATE in a diverse older population in primary care. We will conduct semi-structured interviews with 10 participants, 5 clinicians, and the health coach, to explore factors critical to eventual uptake of MOTIVATE, e.g., acceptability, adoption, sustainability.

Background and Current Practice

Chronic low back pain (cLBP) in older adults is a major public health problem with significant consequences. Annual costs related to back pain exceed \$100 billion, and will rise with the aging population. While the population of older adults is rapidly rising, we lack evidence based options in this population because older adults are often excluded from randomized controlled trials for various reasons including multi-morbidity, polypharmacy, frailty and fragmented social support systems.

My prior work analyzing 13+ years of data shows that older adults are more likely to develop recurrent back pain if they suffer from depressive symptoms. The relationship between cLBP (>3 months) and depression is well established: both are risk factors for the others' onset, influence each other's

treatment, and have adverse reciprocal effects on quality of life, disability, and health care costs. Because cLBP and depression are mutually exacerbating, efforts to improve outcomes for both require effective co-management.

[figure not shown]
Pharmacological management alone has limited effectiveness in older adults. Both cLBP and depression respond well to techniques designed to improve physical/emotional self-management behaviors. Older adults deserve particular attention as there is growing literature that decision making strategies and motivations to change differ from younger populations. Interventions that target age-appropriate motivations, among other behavioral determinants, are ideal for these chronic conditions.

Older adults urgently need effective behavioral interventions that simultaneously target cLBP and depression. Multiple studies demonstrate the effectiveness of non-pharmacological therapies in improving chronic pain outcomes, including therapies based on cognitive behavioral principles and/or movement-based strategies (exercise and physical therapy). We know that physical activity is effective (alone or as augmentation therapy) for adults with depression. A recent publication provides evidence that biopsychosocial multi-component interventions are more effective for patients (average age 45) with cLBP as compared to placebo or physical treatments. However, older adults are consistently excluded from studies for various reasons, mostly having to do with multi-morbidity and polypharmacy. There are no multicomponent tele-based behavioral interventions specifically in older adults with cLBP and depression. Because cLBP and depression are mutually perpetuating and exacerbating, a critical piece of this research is to identify and target interrelated behavioral determinants (i.e., beliefs, fear avoidance, self-efficacy, and motivation) that play a role in older adult's behavior and subsequent outcomes.

Overview of Proposed Intervention

The suggested intervention is grounded in health behavior theories and builds on prior interventions for chronic pain and mental illness in medically complex older adults. Our conceptual model includes patient characteristics, potential reciprocal relationships between the listed constructs, and emphasizes motivation to change as a key behavioral determinant (Figure 1). One-way arrows show that baseline socio-cultural variables, rarely modifiable, influence biopsychosocial factors (i.e. the way an older adult may experience pain) which in turn influence behavioral determinants. The extent and status of specific behavioral determinants may influence/modify specific baseline biopsychosocial factors, as well as both proximal and distal outcomes.

Figure 1: Conceptual Model for Proposed Intervention

Consistent with a recently published model for developing behavioral treatments for chronic diseases, Figure 1 represents a model pathway by which our behavioral intervention is hypothesized to improve behavioral and, ultimately, clinical outcomes. By eliciting and targeting specific behavioral determinants (highlighted box) we will facilitate engagement in a health promoting behavior (physical activity) and ultimately improve cLBP and depression clinical outcomes (disability and depression scores). The behavioral determinants listed in Figure 1 are relevant for both cLBP and depression and include prominent constructs from the health belief model-perceived threat, perceived benefits, barriers, and self-efficacy-as well as from the trans-theoretical model-readiness to change. Consistent with clinical practice, older adults with cLBP and depression exhibit variability in the behavioral determinants listed. To increase intervention potency, the intervention targets both cLBP and depression behavioral determinants and seeks to improve outcomes in both conditions.

Compared to their younger counterparts (aged 49 and younger), older adults appear to be motivated to engage selectively with information that is relevant, positively framed, and fits with their personal goals. For example, when making choices, older adults tend to review and remember relatively more positive than negative information as compared to younger adults. To develop the most robust intervention for this population, we must tailor intervention content recognizing that older adults have unique beliefs, [mis]perceptions, as well as different preferred delivery of the material as compared to younger individuals. Data suggest that positively-framed messages, for instance emphasizing benefits of walking, are more effective than negatively-framed messages, emphasizing risks associated with not walking, in promoting and activating older adults to walk more. Our intervention content and messaging will target these unique motivations to engage in behavioral change.

Health coach delivered behavioral interventions have been shown to be effective in older adults with chronic pain. A health coach, broadly, is defined as a supportive mentor who motivates, educates, and supports clients to achieve their health goals through lifestyle and behavior adjustments. The health coach for this study will have experience with chronic pain and depression. These prerequisites will ensure that the health coach has exposure to principles of motivational interviewing, patient activation, and goal setting. The health coach will receive additional training in motivational interviewing and delivery of the proposed intervention as intended. As proposed in Figure 1, the intervention will be delivered via telephone or video-assisted technology (tele-based) by a health coach using modules that target the listed potential behavioral determinants that specifically focus on how older adults are uniquely motivated to change. The health coach will educate participants, use motivational interviewing to enhance perceived benefits, reduce barriers to participating in recommended behaviors, and assess motivations and readiness to change. Once a participant is ready for action, the health coach will use motivational coaching as well as goal setting and action planning techniques to facilitate behavioral change.

This study protocol is intended to evaluate the tele-based behavioral change intervention in a larger randomized sample.

Study Design

In aim 1, we will assess the feasibility of a tele-delivered behavioral change intervention among older adults (aged 50 and older) with cLBP and depression. Fifty participants will be randomly assigned to one of two groups, behavioral intervention arm (n=25) versus the waitlist control arm (n=25). The active intervention will include eight tele-delivered health coach sessions and three tele-based outcome assessments. Each tele-based outcome assessment is roughly 45-60 minutes, and will be conducted by a member of the research team and will be recorded for research purposes. Each intervention session will be delivered by a trained health coach over a period of 10-20 weeks (up to 5 months total, accounting for additional time between sessions if needed). Aim 2 will involve one, in-depth, telephone-based, semi-structured interview at 6 months post-intervention. The health coach/research coordinator will identify participants who are at higher risk for drop-out, less engaged, or particularly successful at achieving behavioral change. The purpose of this interview is to learn about the barriers and facilitators to successful intervention delivery and integration within primary care, participant retention and acceptability from the clinician, patient, and health coach perspective. We will explore factors that are critical to eventual uptake of MOTIVATE; informed by Proctor's Framework of Implementation Outcomes we will focus on acceptability, adoption, appropriateness and sustainability of MOTIVATE. Semi-structured interviews with patients will be occur over the telephone, while clinician semistructured interviews can occur over the telephone or at a location convenient for the participant-most likely to occur on a UTSW or Parkland location.

The first session will introduce the participant to the health coach and the program, establish rapport, and measure baseline physical activity. The following six sessions address behavioral determinants, followed by a final session designed to be a booster session to the overall program.

An Omron pedometer (product name, Walking style One 2.0; type, HJ-320-E) will be provided to each participant for the assessment of physical activity. The Omron pedometer will be set up by a member of the research team (e.g., stride length, setting date/time) and will be mailed to the participant's home address between sessions one and two. Participants will not be required to mail the Omron pedometer back, nor will they incur out-of-pocket costs if lost, damaged, or stolen. Each participant will receive a courtesy phone call when the pedometer is mailed and will be asked to call the research coordinator when it arrives. The research team will provide technical assistance and instructions to the participant regarding use. The pedometer is intended to be worn on the waist band, daily, with the exception of times when the participant may shower or bathe. The research team will verbally instruct the participant on how to press the mode and memory buttons in order to provide weekly step counts for tracking physical activity. The participants will be prompted by the health coach or research staff to report step counts during subsequent weekly tele-based coaching sessions.

Since we are interested in better understanding feasibility of the intervention as compared to the waitlist control, and how behaviors are sustained over time, the study involves extended follow-up to six months. We will use these extended follow-up data to better understand differential attrition as well as preliminary formative implementation evaluation. Using purposive sampling, we will conduct ~ 16 indepth semi-structured interviews, 10 participants, 5 clinicians, and the health coach. Each interview will occur post-intervention and will include key stakeholders from the following groups: study participants from each arm of the pilot study, the health coach, primary care providers (including clinic leadership, geriatricians, and clinical psychologists- will be identified by the PI's professional network and via snow ball sampling), and will be audio recorded (on LRX 40 USB or UTSW digital logger) for research purposes. Each audio recording will, thereafter, be transferred to a secure folder, behind the UTSW firewall and deleted from the audio recording device. . The research staff will select participants identified as higher risk for drop-out, less engaged, or were particularly successful at achieving behavioral change. The purpose of the final interviews is to learn about the barriers and facilitators to successful intervention delivery and participant retention from the perspectives of the enrolled patients, health coach, and providers. Interview topics will borrow from components of the well-established framework, Promoting Action on Research Implementation in Health Services (PARiHS). Semi-structured interview strategy is informed by two PARiHS dimensions: context-how the microsystem (UTSW and or Parkland) impacts behavioral change uptake, for example, potential facilitators to intervention implementation; facilitation-identifying specific ways to augment the likelihood of implementation. Table 1 outlines the structure of the interview questions.

Table 1. Key Informant Interview Topics Based on PARiHS Framework of Evidence, Context, and Facilitation							
PARiHS Dimension: Evidence	PARiHS Dimension: Context	PARiHS Dimension: Facilitation					
 Perceptions about the strength and motivation for personalized goal-setting Perceptions about how well goal-setting is accepted by adults Perceptions of how goal-setting affects current practices or can be integrated into routine work flows Perceptions of how patient activation can be applied to improve outcomes Perceptions of how motivations to change and identifying meaningful goals can be aligned 	 Availability of resources to carry out personalized goal-setting How training and fidelity assessment for personalized goal-setting fit with work demands Past experiences with collaborating with other health care providers on self-management or goal-setting Existing channels of communication for input and feedback among health care providers regarding goal-setting and self-management 	 How to align roles in the project with existing responsibilities Perceptions about what successful implementation will require from staff, patients, and clinicians Perceptions of skills, attitudes, and beliefs about internal facilitators and study team Plans for establishing formal communication routines between study team, health care providers and other personnel 					

Criteria for Inclusion of Participants

Participant Selection

An initial data pull using patients' electronic medical records (EMR) will identify a pre-screen list of potentially eligible patients. Potential participants will include only those with an International Classification of Diseases-10 (ICD-10) code for back pain and depression. Further eligibility criteria are as follows:

Inclusion Criteria

- Aged 50 and older
- English- speaking
- Working telephone
- Capable of participating in home-based activity
- Chronic low back pain with intensity of 4 or higher on 10 point scale
- At least one doctor visit for cLBP in the two years
- UTSW General Internal Medicine (GIM) or Parkland internal medicine/primary care clinic or community outpatient clinic patient with scheduled clinic appointment within 2 years of enrollment date
- Self-reported low back pain (+/-radiation) in the past 3 months that interferes with daily activities on most days

 Depression, PHQ-9>10 stable (per chart review, no psychotic or suicidal ideation; confirmed over telephone or video-assist)

Exclusion Criteria:

- Aged 49 or less
- No telephone
- Not English speaking
- Unwilling to be randomized to either study arm
- Self-reported, uncorrected hearing or visual disturbance precluding ability to participate in telephone sessions or read pedometer screen
- Cognitive impairment, assessed by Memory Impairment Screen
- Lumbar surgery within the last year
- Self-reported dependence on wheelchair, bed-bound, or severe balance impairment (unable to participate in physical activity intervention)
- Illness requiring hospitalization within the last 3 months (e.g., fall, gout attacks, stroke, heart attack, heart failure, or surgery for blocked arteries)
- Suicidal ideation or prior psychotic episodes requiring hospitalization within the last year

Recruitment Strategy and Informed Consent Process

A waiver of consent for recruitment will be sought for identifying patients in the EMR, delivery of an invitation letter, and screening of potentially eligible participants aged 50 and older with an ICD-10 code for back pain and depression. We are also filing a waiver/alteration of HIPPA request to conduct the tele-delivered intervention and outcome assessments. Such a waiver is justified as minimal risk is anticipated; the waiver will not adversely affect the rights or welfare of participants.

Identified patients will be mailed an invitation letter signed by the principal investigator requesting their participation. The letters will describe the research study, describe what time involvement the project would require, and provide a local number to refuse contact. Letters will only be written in English as non-English speaking patients are ineligible for enrollment.

UTSW Strategy

The first recruitment method involves identifying when potentially eligible participants have appointments in UTSW GIM primary care clinic. The GIM provider will introduce the study and a research staff member to the patient during their clinic visit. The research staff member will then provide a detailed study overview and verbally consent the participant if interested, and ask a series of eligibility screening questions

The second recruitment method involves direct provider referral. [name] will provide a flyer to be posted in GIM primary care clinics (see attached to this IRB protocol submission) with a study synopsis and eligibility criteria. If the participant is interested in learning more, he/she may call the number

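### The pedometer is mailed only after session one, so the intervention arm's step series has no reading from before coaching contact

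*Combined protocol and SAP*

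**What the plan says.** Study Design gives session one three tasks: introduce the coach and the program, "establish rapport, and measure baseline physical activity". It does not name the instrument for the third. The rest of the programme is then set out: "The following six sessions address behavioral determinants, followed by a final session designed to be a booster session". The eight sessions run "over a period of 10-20 weeks (up to 5 months total, accounting for additional time between sessions if needed").

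The same section says that the pedometer "will be provided to each participant for the assessment of physical activity", and that it "will be mailed to the participant's home address between sessions one and two". The participant "will be asked to call the research coordinator when it arrives", and is later prompted to "report step counts during subsequent weekly tele-based coaching sessions".

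Outcome Measures, under Proximal/behavioral outcomes, makes this pedometer the measure of overall activity. It is worn for seven days in a row to yield five complete days. No calendar time point is attached to the wear; the text says only that it is explained at the recruitment call.

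Table 2 shows an Exercise Questionnaire by phone at baseline, mid and end. No step-count row is visible there. Proposed Analyses describes, among intervention recipients, how activity and clinical scores change with the sessions completed, and hopes to learn which sessions are essential.

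**The concern.** A change score needs a starting value from before the exposure. Session one is counted among the coaching sessions, and the device arrives after it. The first step count is therefore taken once contact with the coach has begun, although the plan says that baseline activity is measured in session one.

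Activity is not a peripheral measure. Under Overview of Proposed Intervention, it is the behaviour through which disability and depression are expected to improve: "we will facilitate engagement in a health promoting behavior (physical activity"). If the first post-contact count is used as baseline without a label, any early response to the coach is absorbed into the starting value, and the described change in steps is not a change from before coaching. The pilot is meant to settle procedures for a larger trial, so the same sequence could be carried forward.

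**Working it through.** The main check is the order of events. The documents state no figure for it that could be reproduced.

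**Order of events, intervention arm**
1. Recruitment call: pedometer wear is explained (Outcome Measures). No device is said to be supplied.
2. Baseline assessment by phone: Exercise Questionnaire, RMDQ, PHQ-9 and others (Table 2). No step count is visible.
3. Session one: baseline activity is measured, instrument not named (Study Design).
4. Pedometer mailed; the participant calls when it arrives (Study Design).
5. Earliest possible step count.
6. Session two: content on behavioural determinants begins (Study Design).

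Step 5 follows step 3 for all 25 participants. No visible section supplies a device earlier.

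**Could a wear week fit between sessions one and two?** Eight sessions have 7 gaps. Days left for mailing and set-up = gap between sessions one and two − days of wear. The spacings below are assumptions, since the documents do not fix one.

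| Assumed spacing | Gap, session one to two | Left with 7 days of wear | Left with 5 days |
|---|---|---|---|
| Weekly throughout | 7 days | 0 | 2 |
| Sessions one to seven weekly, booster later | 7 days | 0 | 2 |
| Even over 10 weeks | 70/7 = 10 days | 3 | 5 |
| Even over 20 weeks | 140/7 = 20 days | 13 | 15 |

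Weekly throughout gives 7 × 7 = 49 days, or 7 weeks, which is shorter than the stated 10 to 20 weeks. The late-booster schedule fits: 6 × 7 = 42 days, then a booster gap of 70 − 42 = 28 or 140 − 42 = 98 days. No section describes that schedule, however. So a wear week before session two may or may not fit, and in no case does it precede session one.

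**Delay if the device is mailed first.** Assumed mailing of 2 to 7 days + 7 days of wear = 9 to 14 days. If session one already waits for the binder to arrive (an inference from the binder's use in each session), the added delay is about 7 days.

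**The case against.** The strongest reply is that the sequence works as written. Session one is largely introduction and rapport. A wear week between sessions one and two would still precede the behavioural content, and the plan allows extra time between sessions. Session one could measure activity by self-report, and the Exercise Questionnaire gives an activity baseline in any case. The device instructions submitted to the IRB, the participant manual and Figure 2 are not available here, and any of them might define a baseline step week.

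Most of this stands, and it is why the effect is probably small. It does not remove the point. The mailing time is stated outright, the visible text does not designate a later wear week as baseline, and a questionnaire score cannot serve as the first value of a step series.

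A reader might go further and infer that the late mailing is what prevents the session-by-session analysis from judging session one. The documents do not support that. Steps are reported at later coaching sessions, so nearly everyone who reports them will have had session one. Its separate contribution could hardly be estimated even with an earlier device, and a change around session one would be mixed with the effect of starting to wear a step counter.

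**Conclusion.** The point holds and is minor. On the visible text, the intervention arm's step series has no value from before coaching contact, and the method by which session one measures baseline activity is not stated. The order of mailing is certain from the text. The size of any bias is unknown, and that it is small is a judgement from the content of session one.

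The reach is the step-count part of Proposed Analyses: the description of activity change in intervention recipients and, if the undefined intermediate outcomes include steps, the exploratory comparison from baseline to three months.

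Three stronger readings should be resisted:
- One session in eight (1/8 = 12.5%) precedes the first count. That is a share of sessions, not a measure of harm, because it weights an introductory call equally with the behavioural sessions.
- The 0-day result does not show that wear must run into session two. It depends on spacing that the documents leave open, and nothing says that session two cannot wait for the device.
- Tying step reports to coaching sessions does not show that waitlist counts are omitted. The device goes to every participant, and whether waitlist steps are collected is a matter to clarify, not part of this finding.

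**What to change.** In Study Design, move the mailing to before session one, for example with the binder that Study Procedures already sends to the intervention arm. Complete the seven-day wear before session one takes place, and state that this reading is the step baseline.

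The cost is one earlier mailing of a device already supplied, a wording change, and a delay to session one of about one to two weeks. There is a knock-on effect. Outcome Assessments and Data Collection places the mid and end assessments at about 5 and 10 weeks without stating from when. If they run from the baseline call, a later session one means less coaching before each assessment. In that case, time them from session one and put the waitlist arm on a matching schedule, so that exposure at each assessment does not change.

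If the mailing is not moved, say in Study Design how session one measures activity. In Proposed Analyses, label the first step count as a post-session-one reading and do not call it baseline. This costs only wording, but leaves the step series without a pre-coaching value.

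Under either option, state separately whether step counts are collected in the waitlist arm.
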